**Table 13. Management of Hematologic Adverse Events Associated with TTI-621 Administration**

Note that specific guidelines for management of thrombocytopenia regardless of attribution to TTI-621 and/or doxorubicin are provided in [Table 22](#) and [Table 23](#) and are not described here.

Observation	Management Guidelines
Grade 4 neutropenia lasting > 72 hours	
 
Delay TTI-621 dosing until the re-treatment criterion (ANC <math>> 1.0 \times 10^9/L</math>) is met, then resume TTI-621: 
 
At the same dose if dose delay was <math>\leq 1</math> week
 
One dose level reduction if dose delay was <math>> 1</math> week
 
One dose level reduction if the event recurs
 
 
 

Grade 3 febrile neutropenia lasting > 72 hours Grade 3 neutropenia with clinical evidence of infection Grade 4 febrile neutropenia	
 
Delay TTI-621 dosing until the re-treatment criterion (ANC <math>> 1.0 \times 10^9/L</math>) is met, then resume TTI-621 at one dose level reduction
 

Grade 3 anemia	
 
Delay TTI-621 dosing until resolution to Grade <math>\leq 1</math> or baseline, then resume TTI-621 treatment: 
 
At the same dose if dose delay was <math>\leq 1</math> week
 
One dose level reduction if dose delay was <math>> 1</math> week
 
One dose level reduction if the event recurs
 
 
 

Grade 4 anemia	
 
For Grade 4 events, discontinuation of TTI-621 should be considered. If, per Investigator's assessment, it is in the patient's best interest to continue the treatment, TTI-621 treatment can be resumed when the AE resolves to a level that meets re-treatment criteria
 

**9.2.3.3. Non-Hematologic Events Related to TTI-621 Administration**

TTI-621 dose adjustments based on the occurrence of non-hematologic treatment-related adverse events are described in [Table 14](#).

**Table 14. Management of Non-Hematologic Adverse Events Associated with TTI-621 Administration**

Observation	Management Guidelines
Grade $\geq 3$ events with the following exceptions: 
 
• Nausea and/or vomiting lasting <math><72</math> hours with supportive care
 
• Fatigue lasting <math>\leq 72</math> hours
 
• Laboratory abnormalities lasting <math><72</math> hours and judged by the Investigator as not clinically significant
 
	
 
• For Grade 3 events, delay TTI-621 dosing until the re-treatment criteria are met, then resume TTI-621 at one dose level reduction
 
• No dose reduction is required for the exceptions listed
 
• For Grade 4 events, discontinuation of TTI-621 should be considered. If, per Investigator's assessment, it is in the patient's best interest to continue the treatment, TTI-621 treatment can be resumed when the AE resolves to a level that meets re-treatment criteria
 

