**Table 15. Management of other Treatment-Related Adverse Events**

Severity of Event	Management Guidelines
Grade 1	
 
• Maintain TTI-621 dose level
 
• Provide treatment to control symptoms if applicable
 

Grade 2 (tolerable)	
 
• Maintain TTI-621 dose level
 
• Provide treatment to control symptoms if applicable
 

Grade 2 (intolerable)	
 
• Hold administration of TTI-621 until the adverse event recovers to Grade <math>\leq 1</math> or to baseline level, then resume treatment with TTI-621
 

Grade 3	
 
• Hold administration of TTI-621 until the adverse event recovers to Grade <math>\leq 1</math> or to baseline level, then resume treatment with TTI-621
 

Grade 4	
 
• Discontinue TTI-621 unless patient is receiving clinical benefit, adverse event recovers to baseline level and treating physician recommends continuation of treatment at a lower dose level or under a modified schedule
 

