**9.4. Management of Adverse Events not Attributable to a Specific Study Treatment**

Guidelines for managing adverse events when attribution to either TTI-621 or doxorubicin is not possible in the opinion of the Investigator are provided in [Table 21](#). Guidelines for management of treatment emergent thrombocytopenia are provided in Table 22 and Table 23 in [Section 9.5](#). Discussion with the Sponsor Medical Monitor is recommended to ensure homogeneity in adverse event management across all patients to the extent possible.

**Table 21. General Guidelines for Management of Adverse Events when Attribution is not Possible in the Opinion of the Investigator**

Note that guidelines for management of thrombocytopenia are provided in Table 22 and Table 23 in [Section 9.5](#)

Observation	Management Guidelines

Hematologic Toxicity
 
 
Grade <math>\geq</math> 3 neutropenia (ANC <math>< 1 \times 10^9/L</math>)
 
Grade <math>\geq</math> 3 anemia
 
Hemoglobin <math>< 8 \text{ g/dL}</math>
 
 
Non-Hematologic Toxicity
 
Grade <math>\geq</math> 3 events excluding:
 
 
Sub-optimally treated nausea, vomiting, diarrhea
 
Alopecia
 
Transient fatigue of a duration consistent with that associated with doxorubicin treatment (1-2 weeks)
 
Infusion-related reaction in the absence of described prophylaxis
 
Laboratory abnormalities that are asymptomatic and/or judged by the Investigator as not clinically significant for the patient
 
	
First Appearance
 
 
Delay study treatment until recovery to Grade <math>\leq 1</math> or baseline with ANC <math>> 1.0 \times 10^9/L</math>. If no recovery after a delay of <math>> 21</math> days, discontinue all study treatment.
 
Reduce doxorubicin and TTI-621 dose levels by one dose level.
 
 
First Re-Appearance
 
 
Delay study treatment until recovery to Grade <math>\leq 1</math> or baseline. If no recovery after a delay of <math>> 21</math> days, discontinue all study treatment.
 
Reduce doxorubicin and TTI-621 dose levels by one additional dose level.
 
 
Second Re-Appearance
 
 
Discontinue all study treatment.
 

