<25 x 10  /L	
 
• Omit TTI-621 on Day 8
 
• Monitor platelet recovery (CBC twice weekly recommended)
 
• Consider platelet transfusion per ASCO guidelines if clinically indicated
 
• On Day 1 of next cycle: 
 
○ if platelets have recovered to <math>\geq 75 \times 10^9/L</math>, reduce doxorubicin and TTI-621 each by one dose level and initiate cycle
 
○ if platelets have not recovered to <math>\geq 75 \times 10^9/L</math>, hold doxorubicin and TTI-621 and monitor platelets; initiate the cycle when platelets recover to <math>\geq 75 \times 10^9/L</math> with doxorubicin and TTI-621 each at one dose level reduction
 
 
 
• In the case of a second occurrence of platelet decrease to <25 x 10^9/L, consult with the Sponsor Medical Monitor regarding management
 
• The reduced dose levels of doxorubicin and TTI-621 should be used for the remaining combination cycles
 
• When the subject completes the combination portion of the study and moves to TTI-621 monotherapy: 
 
○ the original TTI-621 dose level should be re-instated and platelet counts monitored
 
○ in the case of platelets < 50 x 10^9/L on D15, hold TTI-621 until platelets are <math>\geq 50 \times 10^9/L</math> and then continue with TTI-621 at a one dose level reduction
 
○ on second occurrence of platelets < 50 x 10^9/L without other causality, reduce TTI-621 by an additional dose level and monitor for tolerability or consult with the sponsor medical monitor regarding management
 
○ in the absence of disease progression, further dose reductions may be implemented after discussion with the sponsor medical monitor.
 
 
 

Day 8 Platelet Count	Management Guidelines

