Day 15 Platelet Count	Management Guidelines
$<\text{LLN} - 75 \times 10^9/\text{L}$	
 
Continue TTI-621 at same dose
 

$<75 \times 10^9 - 50 \times 10^9/\text{L}$	
 
Continue TTI-621 at same dose
 

$<50 \times 10^9 - 25 \times 10^9/\text{L}$ OR Any platelet count with bleeding attributed to study drug treatment	
 
Monitor platelet recovery (CBC twice weekly recommended)
 
Consider platelet transfusion per ASCO guidelines if clinically indicated
 
Hold TTI-621 until platelets are <math>\geq 50 \times 10^9/\text{L}</math> and then continue with TTI-621 at a one dose level reduction
 
On second occurrence of platelets <math>< 50 \times 10^9/\text{L}</math> without other causality, reduce TTI-621 by an additional dose level and monitor for tolerability; in the absence of disease progression, further dose reductions may be implemented after discussion with the Sponsor Medical Monitor
 

$<25 \times 10^9/\text{L}$	
 
Monitor platelet recovery (CBC twice weekly recommended)
 
Consider platelet transfusion per ASCO guidelines if clinically indicated
 
Hold TTI-621 until platelets are <math>\geq 50 \times 10^9/\text{L}</math> and then continue with TTI-621 at a one dose level reduction.
 
On second occurrence of platelets <math>< 25 \times 10^9/\text{L}</math> without other causality, reduce TTI-621 by an additional dose level and monitor for tolerability or consult with the Sponsor Medical Monitor regarding management. In the absence of disease progression, further dose reductions may be implemented after discussion with the Sponsor Medical Monitor.
 

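### Table 14 requires a lower TTI-621 dose after a Grade 3 non-hematologic event but no reduction after a Grade 4 event; Grade 4 anemia in Table 13 has a narrower form of the same gap

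*Protocol*

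**What the plan says.** Protocol Table 14 covers non-hematologic events attributed to TTI-621. Its Grade 3 instruction is definite: "For Grade 3 events, delay TTI-621 dosing until the re-treatment criteria are met, then resume TTI-621 at one dose level reduction". No reduction is needed for the listed exceptions: short-lived nausea, vomiting or fatigue, and brief laboratory changes judged not clinically significant. For Grade 4 the cell first raises discontinuation. If the Investigator judges continuing to be in the patient's interest, then "TTI-621 treatment can be resumed when the AE resolves to a level that meets re-treatment criteria". No dose is given.

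The Grade 4 anemia row of Table 13 has the same structure ("For Grade 4 events, discontinuation of TTI-621 should be considered", then resumption with no dose). The Grade 3 anemia row above it allows the same dose after a delay of one week or less, and requires one level down after a longer delay. It also requires "One dose level reduction if the event recurs".

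Five other places bear on this:

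- Table 10 gives the dose ladder. Below 0.2 mg/kg the entry is discontinuation. Section 9.2.3 allows a lower dose after consultation with the Medical Monitor for a patient who is benefiting.
- Section 9.2.1, on interruptions, says the TTI-621 dose level need not be modified at restart.
- Table 21 covers Grade 3 or worse events that cannot be attributed to one agent. At first appearance it says: "Reduce doxorubicin and TTI-621 dose levels by one dose level".
- Table 15, for other Grade 4 events, allows continuation only where the "treating physician recommends continuation of treatment at a lower dose level or under a modified schedule".
- Section 5.3 ends treatment for a treatment-related event judged life-threatening, whatever its grade. Its exception covers only events attributed to doxorubicin.

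**The concern.** A dose-modification rule should not become less demanding as the event becomes more severe, or as the drug's responsibility becomes clearer. In Table 14 the Grade 3 patient must go down a level, while the Grade 4 patient may return at the original dose. Compared with Table 21, a site that can name TTI-621 as the cause has no required reduction, while a site that cannot decide must reduce both drugs.

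What is at stake is patient safety at re-exposure and consistent handling across up to 20 centers. The case matters most at 0.2 mg/kg, the dose anticipated for expansion Cohort A (31 patients planned), because one level down from there is a stop.

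**Working it through.** The plan states no figure to reproduce. The check sets the rows side by side and traces one patient through them.

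**Rows covering Grade 4 events or the lowest platelet band (infusion reactions, Table 12, set aside)**

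| Row | TTI-621 dose at resumption |
|---|---|
| Table 13, Grade 4 neutropenia over 72 h | Same if delay is one week or less; one level down if longer or recurrent |
| Table 13, Grade 4 febrile neutropenia | One level down |
| Table 13, Grade 4 anemia | Not stated |
| Table 14, Grade 4 non-hematologic | Not stated |
| Table 15, Grade 4 other events | Lower level or modified schedule |
| Table 21, Grade 3 or worse, cause unclear | One level down, both drugs |
| Table 22, platelets below 25 x 10^9/L | "with doxorubicin and TTI-621 each at one dose level reduction" |
| Table 23, platelets below 25 x 10^9/L | "and then continue with TTI-621 at a one dose level reduction" |

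Six of the eight rows give a dose instruction and two do not. Table 12 is left out because infusion reactions are managed by rate and prophylaxis; its Grade 4 row also names no dose, so counting it would give six of nine.

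**Trace at 0.2 mg/kg, event attributed to TTI-621 unless noted**

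- Table 14, Grade 3: one level down, which Table 10 makes discontinuation unless the Section 9.2.3 exception applies.
- Table 14, Grade 4, not deemed life-threatening: may resume. Without the exception, 0.2 mg/kg is the only level available.
- Table 13, Grade 3 anemia, delay of one week or less: resumes at 0.2 mg/kg. There is no inversion here.
- Table 13, Grade 3 anemia, delay over one week or recurrence: discontinuation by default.
- Table 13, Grade 4 anemia, not deemed life-threatening: may resume, dose unstated.
- Table 21, Grade 3 or 4 anemia or a non-excluded non-hematologic event, cause unclear: one level down at first appearance, so discontinuation of TTI-621 by default.

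**Size of the dose difference (Table 10).** Ratio = highest dose left open after Grade 4 / dose required after a Grade 3 non-hematologic event.

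- From 2.0 mg/kg: 2.0/1.4 = 1.43, or 43% higher.
- From 1.0 mg/kg (the added expansion dose, SAP 4.3.2): 1.0/0.7 = 1.43, or 43% higher.
- From 0.7 mg/kg: 0.7/0.5 = 1.40, or 40% higher.
- From 0.2 mg/kg: 0.2 against a default stop.

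**Frequency.** The documents give no Grade 4 counts. In TTI-621-01 (Protocol 3.5.2.1.2), related anemia of Grade 3 or worse occurred in 20 of 235 patients (20/235 = 8.5%), so Grade 4 related anemia there lies between 0 and 20 of 235. Carried over to 62 expansion patients this is 0 to 0.085 x 62 = 5.3. That range rests on an unsupported assumption: TTI-621-01 used weekly dosing, was largely hematologic, and had more related anemia in its AML and Hodgkin cohorts. No comparable range can be formed for Table 14, where the inversion is clearest.

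**The case against.** **Section 5.3 already stops the serious cases.** The generic scale in Section 13.4 describes Grade 4 as life-threatening, so many such patients will stop. This stands, and it shrinks the affected group. It does not close the gap, because Section 5.3 turns on a judgement separate from grade, and Tables 13 and 14 still provide for Grade 4 resumption. If every Grade 4 event were life-threatening, that resumption text would contradict Section 5.3.

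**The protocol is not silent on dose.** Section 9.2.1 says no change is needed at restart. The sentence follows text on holds longer than 42 days, so its reach is arguable. Read narrowly, it leaves the dose unstated; read generally, it expressly permits full dose. The inversion survives both readings.

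**Laboratory events.** The Synopsis says asymptomatic laboratory abnormalities should generally not lead to dose changes unless clinically significant or life-threatening. Table 14 exempts brief ones and Table 21 excludes asymptomatic ones. This narrows the group further.

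**Investigator discretion.** Tables 13 and 14 raise discontinuation first at Grade 4. Table 21 does so at first appearance only if recovery takes more than 21 days. It is therefore fair to call the attributed-event rule looser on dose, but not looser in every respect. Investigators may also reduce the dose on their own judgement.

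**A stronger reading to avoid.** A reader might infer that all Grade 3 events carry a reduction and that any Grade 3 patient at 0.2 mg/kg stops. The documents do not support this. Grade 3 anemia with a delay of one week or less resumes at the same dose, the Grade 3 row of Table 15 states no reduction, and Table 12 says a Grade 3 infusion reaction needs none.

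**Conclusion.** The point holds, centred on Table 14: one level down is mandatory after a Grade 3 non-hematologic event outside the listed exceptions, and no reduction is required after a Grade 4 event. At 0.2 mg/kg this is a default stop against possible continuation. The stop is not absolute, given Section 9.2.3, and the continuation applies only to events not deemed life-threatening. For anemia the gap is narrower: against Grade 3 anemia it appears only after a delay over one week or a recurrence, and against Table 21 it appears at first appearance.

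Where a lower level exists among the doses traced above, the permitted restart dose is 40% to 43% above the dose required after the milder non-hematologic event. The number of patients affected is unknown and, given Section 5.3, probably small. A reader might infer consequences for response rate or the Simon design; nothing in the documents supports that, and none is claimed. Severity is minor: a dosing-safety inconsistency that sites could apply differently.

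**What to change.** In the Grade 4 text of Table 14 and the Grade 4 anemia row of Table 13, replace the resumption clause with: *Subject to Section 5.3, TTI-621 may restart at one dose level reduction once the re-treatment criteria are met; at 0.2 mg/kg, discontinue unless the Section 9.2.3 exception applies.* Keep the Table 14 exceptions as they are. In Section 9.2.1, qualify the restart sentence with: *unless Tables 13–15 or 21–23 require a reduction.*

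Tying Grade 4 anemia to the Grade 3 anemia rule would not be enough, because that rule requires no reduction when the delay is one week or less.

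The cost is wording in two table cells and one clause. Visits, sample size and the SAP are unchanged. The real downside is at 0.2 mg/kg, the anticipated Cohort A dose: the change adds a default stop after Grade 4 events that the present text lets patients continue past. That matches the existing Table 14 rule for Grade 3 and is softened by the Medical Monitor exception, but it should be stated openly when the change is made.

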**9.2.3.4. Management of Other Adverse Events Related to TTI-621 Administration**

TTI-621 dose adjustments based on the occurrence of other treatment-related adverse events are described in [Table 15](#).

**Table 15. Management of other Treatment-Related Adverse Events**

Severity of Event	Management Guidelines
Grade 1	
 
• Maintain TTI-621 dose level
 
• Provide treatment to control symptoms if applicable
 

Grade 2 (tolerable)	
 
• Maintain TTI-621 dose level
 
• Provide treatment to control symptoms if applicable
 

Grade 2 (intolerable)	
 
• Hold administration of TTI-621 until the adverse event recovers to Grade <math>\leq 1</math> or to baseline level, then resume treatment with TTI-621
 

Grade 3	
 
• Hold administration of TTI-621 until the adverse event recovers to Grade <math>\leq 1</math> or to baseline level, then resume treatment with TTI-621
 

Grade 4	
 
• Discontinue TTI-621 unless patient is receiving clinical benefit, adverse event recovers to baseline level and treating physician recommends continuation of treatment at a lower dose level or under a modified schedule
 

**9.3. Management of Adverse Events Associated with Doxorubicin****9.3.1. Doxorubicin Treatment Interruptions**

Treatment with doxorubicin may be temporarily suspended for up to 42 days to allow for resolution of adverse events. Dose interruptions for reason(s) other than toxicity and re-treatment may be allowed in accordance with standard of care if the patient is receiving clinical benefit and after discussion with the Sponsor Medical Monitor. In general, if an interruption of more than 42 days is required due to adverse events, doxorubicin will be permanently discontinued; however, if in the judgment of the Investigator, the patient is likely to derive clinical benefit from doxorubicin after a hold of more than 42 days, study drug may be re-started with approval of the Sponsor Medical Monitor. Longer interruptions may be

acceptable on a patient-by-patient basis at the discretion of the Investigator after discussion the Sponsor Medical Monitor.

### 9.3.2. Doxorubicin Re-Treatment Guidelines for Day 1

The laboratory parameters described in [Table 16](#) should be met for re-treatment with doxorubicin.

**Table 16. Requirements for Re-Treatment with Doxorubicin on Day 1 (Cycle 2 through Cycle 6)**

Parameter	Criterion
Platelets	$\geq 75 \times 10^9/L$
ANC	$\geq 1 \times 10^9/L$
Organ toxicity or other treatment-related adverse event	Grade $\leq 2$
Bilirubin	$\leq 1.5 \times ULN$
AST, ALT	$\leq 3 \times ULN$ ( $< 5 \times ULN$ if liver metastases)

### 9.3.3. Doxorubicin Dose Modification Guidelines

In general, doses should not be reduced for Grade 1 or Grade 2 adverse events, but treatment to manage symptoms should be provided, if applicable.

For the purposes of doxorubicin dose modification in response to adverse events, the dose modification schema presented in [Table 17](#) will be used.

**Table 17. Doxorubicin Dose Modifications**

Dose Level	Doxorubicin Dose
Dose Level 1	75 mg/m 
Dose Level -1	60 mg/m 
Dose Level -2	45 mg/m 

General guidelines for dose modifications in response to observed adverse events in presented in [Table 18](#). In consideration that doxorubicin is being used as a standard of care anti-cancer therapy in the enrollment patient population and based on Investigator and site experience with doxorubicin in the enrolled patient population, alternate dose modifications may be implemented after discussion with the Sponsor Medical Monitor.

**Table 18. Doxorubicin Dose Modification Guidelines**

Worst Toxicity in Prior Cycle	Doxorubicin Dose for Next Cycle
Febrile neutropenia	
Thrombocytopenia with bleeding	Decrease doxorubicin one dose level
ANC Grade 4 for $\geq$ 7 days	
Cardiotoxicity, including any signs and symptoms of heart failure, greater than 10% decline in LVEF to below the LLN, greater than 20% decline in LVEF from any level, or LVEF $\leq$ 45%	Discontinue doxorubicin Consider initiation of dexrazoxane
Grade 3 organ toxicity	Decrease doxorubicin one dose level
Grade 4 organ toxicity	Discontinue doxorubicin
Hepatic impairment	
Serum bilirubin 1.5 – 3.0 mg/dL	50% dose reduction
Serum bilirubin 3.1 – 5.0 mg/dL	75% dose reduction
Serum bilirubin $>$ 5.0 mg/dL	Discontinue doxorubicin

### 9.3.3.1. Cardiac Toxicity Related to Doxorubicin Administration

Cardiotoxicity is a recognized risk of doxorubicin that increases with higher cumulative drug exposure. Cardiac monitoring is conducted by a combination of monitoring of clinical parameters, ECG and echocardiogram (ECHO) / multigated acquisition (MUGA) scan. ECG changes, arrhythmias, tachycardia, and/or chest pain should be managed according to clinical practice based on the specific findings.

Patients will undergo baseline LVEF determination by ECHO or MUGA scan. This evaluation may be repeated at any time during the study if clinically indicated. A decrease in LVEF of  $\geq$  10% and below the lower limit of normal, or an absolute decrease of 20%, or if the absolute LVEF decreases to or below 40%, doxorubicin will be discontinued. Doxorubicin should also be discontinued if the patient develops Grade  $\geq$  3 left ventricular systolic dysfunction (symptomatic congestive heart failure).

If doxorubicin is discontinued for the above changes in LVEF despite optimal prophylaxis, the patient may be eligible to continue on study with TTI-621 monotherapy after discussion with the Sponsor Medical Monitor, provided that the patient has completed at least four cycles of doxorubicin therapy, is receiving clinical benefit and meets guidelines for re-treatment with TTI-621.

The diagnostic method used at baseline for cardiovascular assessments (for example ECHO or MUGA scans) should be the same method used throughout the study, unless there is clinical or instrumental evidence that further investigations are needed.

The use of dexrazoxane to reduce the incidence and severity of cardiomyopathy due to doxorubicin administration in patients who have received a cumulative doxorubicin dose of 300 mg/m^2 and who will continue to receive doxorubicin is recommended and will be implemented in this study. As described in [Section 5.2.1.1](#), prophylaxis with dexrazoxane for cardiotoxicity must begin no later than with initiation of Cycle 5 when cumulative doxorubicin will have reached 300 mg/m^2. Do not administer dexrazoxane as a cardioprotectant at the initiation of doxorubicin treatment unless that is the standard of care at a particular institution.

Doxorubicin can result in arrhythmias, including life-threatening arrhythmias, during or within a few hours after doxorubicin administration and at any timepoint during treatment. Tachyarrhythmias, including sinus tachycardia, premature ventricular contractions and ventricular tachycardia, as well as bradycardia may occur. Electrocardiographic changes including non-specific ST-T wave changes, atrioventricular and bundle-branch block can also occur. These electrocardiographic changes may be transient and self-limited and may not require dose modifications of doxorubicin.

